8.3.4.2. Secondary Endpoints

Each secondary effectiveness endpoint will be summarized using counts and percentages and an exact 95% confidence interval for the true percentage based on the binomial distribution. The secondary effectiveness endpoints, except the rate of donor liver utilization, will be analyzed using the PP population as primary analysis and using the mITT population as sensitivity analysis.

8.3.4.3. Other Endpoints

The proportion of patient and graft survival at day 30, 6 months, 12 months, 24 months, 36 months, 48 months and 60 months will be calculated with 95% confidence interval.

The other endpoints will be analyzed with both PP population and mITT population.

8.4. Safety Analysis

The safety endpoint will be summarized using descriptive statistics. A 95% confidence interval for the mean based on the t-distribution will be presented.

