4.3.4. Safety Endpoint

Safety will be analyzed by examination of the frequency of liver graft-related serious adverse events (LGRSAEs) up to the 30-day follow-up after transplantation. This endpoint is defined as the average number of liver graft-related serious adverse events through the 30 days post-liver transplant (per subject, consisting of the following events; at most one per type per person):

- Primary non-function (defined as irreversible graft dysfunction requiring emergency liver re-transplantation or death, in the absence of immunologic or surgical causes)
- Ischemic biliary complications (ischemic biliary strictures, and non-anastomotic bile duct leaks)
- Vascular complications (non-surgical hepatic artery stenosis, hepatic artery thrombosis and portal vein thrombosis)
- Liver graft-related coagulopathy
- Liver allograft infections (liver abscess, cholangitis, etc.).

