8.2.2. Modified Intent-to-Treat Population

The modified Intent-to-Treat (mITT) population will include subjects who are transplanted in the study with a liver preserved on OCS Liver System. The mITT population will be used for the sensitivity analysis of effectiveness. The safety analysis will also be based on the mITT population.

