8.6. Sample Size Determination

Sample size calculations are based on the following specifications:

- Comparison to Objective Performance Goal (OPG)
- Endpoint is 6-month graft survival
- One-sided, exact binomial confidence interval
- Alpha = 0.025
- Power = 80%
- True proportion = 0.88
- Objective Performance Goal = 0.765.

Based on the above specifications, a sample size of 101 transplanted subjects with DCD donor liver preserved on OCS Liver System is required. The sample size will be increased to 130 to allow for a sufficient number of subjects in the per protocol population.

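### If graft-related serious events are sparse, the planned t-interval for their mean count covers less than 95% and its upper limit is usually what falls short; the interval is descriptive, so no decision is affected

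*Combined protocol and SAP*

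**What the plan says.** Section 4.3.4 defines the variable: "This endpoint is defined as the average number of liver graft-related serious adverse events through the 30 days post-liver transplant", counted per subject and "consisting of the following events; at most one per type per person". Five event types are listed: primary non-function, ischemic biliary complications, vascular complications, graft-related coagulopathy and allograft infections. Each subject therefore contributes an integer from 0 to 5. The synopsis makes this the principal safety analysis.

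Section 8.4 plans descriptive statistics and one interval: "A 95% confidence interval for the mean based on the t-distribution will be presented". The synopsis row on safety analysis says the same. On the population, section 8.2.2 states: "The safety analysis will also be based on the mITT population". On its size, section 8.6 states: "The sample size will be increased to 130 to allow for a sufficient number of subjects in the per protocol population".

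The documents give no expected LGRSAE rate, no safety performance goal, no safety hypothesis and no rule for the case of no events. By contrast, sections 8.3.4.1 and 8.3.4.2 use exact binomial intervals for the primary and secondary effectiveness endpoints, and section 8.7 uses an exact lower bound for the stopping rule.

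**The concern.** A t-interval is symmetric about the sample mean and takes its width from the sample standard deviation. With a sparse, right-skewed count, a sample that happens to contain few events has both a low mean and a small standard deviation. The interval is then too low and too short together. The misses fall mostly on one side, with the upper limit below the true event rate. The lower limit can also be negative, and with no events the interval shrinks to a point.

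In a single-arm trial, readers use the upper limit of this interval to judge how much harm remains compatible with the data. At stake is how that limit is reported and read.

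**Working it through.** **Inputs.** n = 130 (section 8.6). Per-subject count 0 to 5 (section 4.3.4). Two-sided 95% t-interval (section 8.4). The true mean is not in the documents, so it is assumed over 0.01 to 0.50. Clustering of event types within a patient is also assumed, with correlation rho of 0, 0.05 or 0.2.

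**The plan's own figure.** The safety endpoint has none to reproduce. The only computed sample size belongs to the primary endpoint: "a sample size of 101 transplanted subjects with DCD donor liver preserved on OCS Liver System is required", from a "One-sided, exact binomial confidence interval" with "True proportion = 0.88", goal 0.765 and alpha 0.025. It reproduces. At n = 100 power is 78.4%; at n = 101 the rule is at least 86 successes, with actual alpha 0.0226 and power 85.0%, and power stays at or above 80% from there (checked to n = 300). It matters here only for the choice of n.

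**One sample by hand.** The interval is m ± t × s/√n, with t(0.975, 129) = 1.9785. Take 3 events in 3 different subjects:

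- m = 3/130 = 0.0231
- s = √[(130/129) × 0.0231 × 0.9769] = 0.1507
- half-width = 1.9785 × 0.1507/√130 = 0.0262
- t-interval: -0.3% to 4.9%
- exact binomial (Clopper-Pearson): 0.5% to 6.6%

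The two are comparable because, with at most one event per subject, the mean count equals the proportion affected. With 0 events, s = 0 and the t-interval is the single point 0; the exact interval runs up to 2.8%.

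**Coverage, exact enumeration, at most one event per subject.** The number of events K is binomial(130, μ). The upper t-limits for K = 0, 1, 2, 3 are 0, 0.0229, 0.0368 and 0.0492. At μ = 0.01 the upper limit is too low only when K = 0, with probability 0.99^130 = 0.271. At μ = 0.05 it is too low when K ≤ 3, with probability 0.106.

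| True mean | Expected events | Coverage | Upper limit too low | Lower limit too high |
|---|---|---|---|---|
| 0.01 | 1.3 | 72.9% | 27.1% | 0.04% |
| 0.02 | 2.6 | 92.6% | 7.2% | 0.1% |
| 0.03 | 3.9 | 89.8% | 9.6% | 0.6% |
| 0.04 | 5.2 | 89.0% | 10.4% | 0.6% |
| 0.05 | 6.5 | 88.9% | 10.6% | 0.6% |
| 0.10 | 13 | 94.4% | 4.6% | 1.0% |
| 0.20 | 26 | 94.1% | 4.6% | 1.3% |
| 0.30 | 39 | 95.3% | 3.2% | 1.5% |

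For the means from 0.01 to 0.05 shown, 94 to 99.9% of misses have the upper limit too low. Coverage oscillates between the tabulated values. Over 0.02 to 0.05 it averages 90.4%, ranging from 80.0% to 95.2%. At n = 101 and mean 0.05 it is 88.1%.

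**Counts of 0 to 5, with and without clustering.** Simulation with 200,000 trials per setting, n = 130; clustering is beta-binomial across the five types. The alternative is a quasi-Poisson score interval. It solves (m - μ)² = z²φμ/n, giving m + c/2 ± √(cm + c²/4), with c = z²φ/n and φ = s²/m, and φ set to 1 when no event occurs.

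| True mean | t, rho 0 | Score, rho 0 | t, rho 0.05 | Score, rho 0.05 | t, rho 0.2 | Score, rho 0.2 |
|---|---|---|---|---|---|---|
| 0.01 | 72.7% | 95.8% | 69.4% | 96.4% | 60.2% | 96.0% |
| 0.02 | 92.5% | 95.5% | 90.5% | 96.2% | 84.1% | 96.2% |
| 0.03 | 89.5% | 94.0% | 87.6% | 93.8% | 81.3% | 90.1% |
| 0.05 | 88.5% | 95.7% | 87.1% | 95.1% | 83.9% | 92.4% |
| 0.10 | 93.7% | 94.1% | 92.4% | 94.0% | 89.9% | 93.1% |
| 0.30 | 94.4% | 94.7% | 94.3% | 94.7% | 93.6% | 94.5% |

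In the three-event sample above, φ = 0.1507²/0.0231 = 0.984 and the score interval is 0.8% to 6.7%. With no events it is 0 to 3.0%.

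**The case against.** **Sparsity is assumed, and the documents may point the other way.** These are seldom-used livers. The introduction reports poor early DCD experience. The sample size assumes 12% graft failure at 6 months, and the endpoint sums five event types. A mean of 0.10 needs only 13 events in 130 subjects. This stands: none of it fixes the 30-day LGRSAE rate, but it prevents any statement that the interval will be poor. The finding is conditional.

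**Nothing depends on the interval.** This also stands. There is no LGRSAE threshold or test. A reader might infer that the trial's safety conclusion is unsound or that an error rate is inflated. The documents do not support that, because the interval is only presented.

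**The gravest events are covered elsewhere.** Early allograft dysfunction or primary non-function, and ischemic cholangiopathy at 6 months, get exact binomial intervals. Deaths and primary non-function are monitored under section 8.7. This stands in part: those analyses use other definitions, time points or purposes, and none gives an interval for the LGRSAE mean.

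**Replacements can fail too.** This is correct and shapes the fix. With no events the estimated dispersion is 0/0, and a bootstrap of all zeros returns the point 0. An exact Poisson interval on the total count covers only 86 to 96% when types cluster at rho 0.2. Any replacement needs a stated zero-event rule.

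**Conclusion.** The point holds as a conditional, minor one. If the true mean is at or below about 0.05 events per subject, the planned interval usually covers less than its nominal 95%. At means of 0.02 to 0.05 the upper limit is too low in about 7 to 11% of trials, against the 2.5% that a balanced two-sided interval would have. Clustering makes this worse: at a mean of 0.05, coverage falls to about 87% at rho 0.05 and 84% at rho 0.2.

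At means of 0.10 or more with independent types, the shortfall is about a percentage point or less and the gain from changing is small. Only fairly strong clustering carries the problem further (about 90% at mean 0.10, rho 0.2).

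The rate and the correlation are assumptions, since the documents give neither. A reader might take the result to mean that the device's harm will be understated. The documents do not support that: they do not show that events will be sparse, and they attach no decision to the limit.

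**What to change.** In section 8.4, the synopsis row on safety analysis and the SAP text:

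1. Add exact binomial (Clopper-Pearson) 95% intervals for the proportion of mITT subjects with at least one LGRSAE and for each of the five event types. At n = 130 these cover 95.6 to 99.0% for true rates of 0.01 to 0.30. They are not affected by clustering of types within a patient. They are worth having whatever the total rate, because each type is sparser than the total.
2. For the mean count, replace the t-interval with the quasi-Poisson score interval, and state that the dispersion is set to 1 when no event occurs. It covers about 94 to 96% with independent types. At rho 0.2 it covers about 90 to 96%, which is imperfect but better than the t-interval at every mean tested.
3. Do not use a bootstrap as the replacement, because it is degenerate when no event occurs.

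The cost is a slightly higher upper limit (6.7% instead of 4.9% in the three-event sample) and a few lines of code. No new data are needed. Section 8.3 allows the SAP to be finalised up to database lock, so the change can be made there.

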8.5. Treatment of Missing Data

A tipping point analysis of the primary endpoint will be performed in the following manner for the PP population and mITT population. Initially the analysis will be performed with all missing values for the primary endpoint defined to be successes (i.e., not graft failures). If this analysis results in rejection of the null hypothesis, the analysis will continue by setting one missing value to be a graft failure and all of the other missing values to be successes. This procedure will continue in the same manner, each time setting one additional missing value to be a failure, until the first time that the analysis does not result in rejection of the null hypothesis. This point is referred to as the tipping point, the point at which conclusions change from being favorable to the treatment to being unfavorable.

No other data imputation is planned for effectiveness and safety measures.

8.6. Sample Size Determination

Sample size calculations are based on the following specifications:

- Comparison to Objective Performance Goal (OPG)
- Endpoint is 6-month graft survival
- One-sided, exact binomial confidence interval
- Alpha = 0.025
- Power = 80%
- True proportion = 0.88
- Objective Performance Goal = 0.765.

Based on the above specifications, a sample size of 101 transplanted subjects with DCD donor liver preserved on OCS Liver System is required. The sample size will be increased to 130 to allow for a sufficient number of subjects in the per protocol population.

8.7. Stopping Rule

The following stopping rules are to be used in the study:

1. Stop the study if and when there are 4 deaths before Day 30 or initial hospital discharge post-transplant (whichever is later) among the first 10 recipients; or
2. Stop the study if and when there are 4 incidences of primary non-function within the first 7 days post-transplant among the first 10 recipients; or
3. Stop the study if and when there are 7 deaths before Day 30 or initial hospital discharge post-transplant (whichever is later) among the first 20 recipients; or
4. Stop the study if and when there are 7 incidences of primary non-function within the first 7 days post-transplant among the first 20 recipients.

This rule is based on the following: Let p denote the true proportion of recipients transplanted with an OCS-preserved liver for whom the recipient does not survive until Day 30 or initial hospital discharge post-transplant (whichever is later) or let p denote the true proportion of recipients transplanted with an OCS-preserved liver for whom the recipient experiences primary non-function of the graft within the first 7 days post-transplant. Stop the study (based on 10 or 20 recipients) if there is statistical evidence that the true value of p exceeds 0.12, i.e., if the exact 97.5% lower confidence bound for p exceeds 0.12 (12%). The above statistical stopping rules would be applied to all combinations of number of deaths and incidences of PNF and number of recipients that were observed in the study.

TransMedics will be responsible for implementing the stopping rule and will notify the DSMB as if the stopping rules are met. In addition, the DSMB will review the rules at the scheduled DSMB meetings.

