13.9. Data Safety Monitoring Board

An independent Data Safety Monitoring Board (DSMB) will be established by the Sponsor to periodically assess the progress of the trial, the safety data and the primary effectiveness and safety endpoints. The DSMB will make recommendations to the Sponsor regarding continuation, modification or termination of the clinical trial. Further details on member responsibilities and frequency/scheduling of DSMB meetings are contained in the DSMB charter.

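### Section 8.7 is inconsistent about how far its stopping rule reaches: the first 20 recipients, or every event and recipient count in the study

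*Combined protocol and SAP*

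**What the plan says.** Section 8.7 of the combined protocol and SAP gives four triggers, two for each event type. For primary non-function (PNF) the first is "Stop the study if and when there are 4 incidences of primary non-function within the first 7 days post-transplant" among the first 10 recipients. For deaths the second is "7 deaths before Day 30 or initial hospital discharge post-transplant (whichever is later) among the first 20 recipients". The other two are 4 deaths in the first 10 and 7 cases of PNF in the first 20.

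The section then explains where the counts come from. With p the true rate of the event, it says: "Stop the study (based on 10 or 20 recipients) if there is statistical evidence that the true value of p exceeds 0.12", meaning that the exact 97.5% lower confidence bound for p is above 0.12. The next sentence says the rules would be "applied to all combinations of number of deaths and incidences of PNF and number of recipients that were observed in the study".

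The sponsor implements the rule and notifies the DSMB if it is met; in addition, "the DSMB will review the rules at the scheduled DSMB meetings". Section 13.9 has the DSMB "periodically assess the progress of the trial, the safety data and the primary effectiveness and safety endpoints", and says that details on "frequency/scheduling of DSMB meetings are contained in the DSMB charter". The charter is not among the documents supplied. Section 4.2 sets the trial size at up to 130 transplanted recipients.

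**The concern.** The triggers and the parenthesis in the criterion end the rule at recipient 20. The sentence that follows carries it through the whole study. Nothing says that 10 and 20 are examples, which statement governs, what the thresholds are at other counts, or how often the bound is to be checked.

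This is the only numerical stopping rule in the supplied documents, and the sponsor operates it. If events accumulate after recipient 20, the sponsor would have to settle the scope with the events already in view. A prespecified rule is meant to prevent exactly that. At stake is whether a numerical threshold binds for recipients 21 to 130.

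**Working it through.** **Inputs.** From section 8.7: triggers 4/10 and 7/20, and an exact one-sided 97.5% lower bound compared with 0.12. From section 4.2: up to 130 recipients. Assumed, because the documents do not say: recipients are independent; each outcome is known at once; about 20 of the 130 outcomes are still pending when enrolment ends, so the last useful look is at 110. The true rates of 8%, 15% and 20% are illustrative; only 12% comes from the plan.

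**Step 1: reproduce the plan's thresholds.** For x events in n recipients the exact lower bound L(x, n) is the 2.5th percentile of Beta(x, n − x + 1). It exceeds 0.12 exactly when P(X ≥ x), with X ~ Binomial(n, 0.12), is below 0.025.

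- n = 10: L(3, 10) = 0.0667 (tail 0.1087); L(4, 10) = 0.1216 (tail 0.0239). The smallest stopping count is 4.
- n = 20: L(6, 20) = 0.1189 (tail 0.0260); L(7, 20) = 0.1539 (tail 0.0067). The smallest stopping count is 7.

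Both agree with the plan.

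**Step 2: apply the same bound beyond 20.**

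| n | Smallest stopping count | L at that count | L at one fewer |
|---|---|---|---|
| 30 | 8 | 0.1228 | 0.0993 |
| 40 | 10 | 0.1269 | 0.1084 |
| 50 | 12 | 0.1306 | 0.1153 |
| 60 | 13 | 0.1207 | 0.1078 |
| 70 | 15 | 0.1252 | 0.1139 |
| 80 | 17 | 0.1289 | 0.1189 |
| 90 | 18 | 0.1231 | 0.1141 |
| 100 | 20 | 0.1267 | 0.1184 |
| 110 | 21 | 0.1222 | 0.1147 |

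Read literally, the broad sentence also adds stops inside the first 20: 2/2 (0.158), 3/5 (0.147), 5/14 (0.128) and 6/19 (0.126).

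**Step 3: when the scopes disagree.** At 8/30 the broad scope stops. The list does not, provided at most 3 events fell in the first 10 and at most 6 in the first 20. If all placements of the events among the recipients are equally likely, a listed trigger would already have fired in about 55% of 5/14 placements, 30% of 8/30, 23% of 12/50 and 12% of 21/110. In the remainder the two scopes give opposite decisions.

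**Step 4: stop probabilities, one endpoint.** Let f_n(k) be the probability of k events after n recipients with no stop so far. Then f_n(k) = f_{n−1}(k)(1 − p) + f_{n−1}(k − 1)p, and the mass with k at or above the threshold of the current block of 10 is moved to stopped. Counts never fall, so stopping when a block's threshold is reached gives the same probability as looking at the end of each block.

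| True rate | List only | Every 10 to 110 | Every recipient to 110 |
|---|---|---|---|
| 8% | 0.6% | 0.8% | 1.9% |
| 12% | 2.7% | 7.5% | 11.1% |
| 15% | 6.0% | 25.1% | 31.0% |
| 20% | 15.7% | 72.1% | 76.4% |

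At 20%, the every-10 rule has stopped with probability 28.4% by recipient 30, 50.0% by 60 and 64.0% by 90.

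**Step 5: sensitivity to the last look.** If 40 outcomes are pending, the last look is at 90, and the every-10 figures become 6.9% at 12% and 64.0% at 20%. With looks to 130 they are 8.0% and 78.4%.

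**The case against.** The paragraph can be read coherently: a general criterion, four worked thresholds, then a statement that the criterion applies at every count. On that reading the listed triggers are a subset of the broader rule, since 4/10 and 7/20 come from the same bound, and a sponsor following the broad sentence breaks nothing. This stands. A reader might infer that the sponsor cannot comply with both statements; the documents do not support that. What remains is that the parenthesis restricts the criterion itself, and that the broad sentence has neither thresholds nor a checking schedule.

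A narrower reading is that the sentence only crosses the two event types with 10 and 20 recipients. It fits poorly, because the sentence also varies the number of recipients observed in the study.

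A reader might also infer that recipients 21 to 130 go unmonitored. Sections 8.7 and 13.9 rule that out: the DSMB reviews safety data and these rules throughout, and may recommend termination. But it reviews the same ambiguous text, and any clarification in the charter cannot be seen here.

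Finally, the size rests on rates and a last look that the documents do not give, and the death endpoint is not known at once: it runs to Day 30 or discharge, whichever is later. A stop for deaths would therefore come after more transplants than the immediate-outcome calculation implies.

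**Conclusion.** The inconsistency is real and should be fixed. The thresholds in the list are right; the scope is unsettled, and on some data the two scopes give opposite decisions. The size depends on the true rate. At 8% the choice hardly matters (0.6% against 0.8% per endpoint). At 12% it is 2.7% against 7.5%, and at 20% it is 15.7% against 72.1%. These figures assume independent recipients, immediate outcomes, looks every 10 recipients and a last look at 110; the 8% and 20% rates are illustrative. The primary effectiveness test is not affected. The point concerns which numerical rule binds the sponsor after recipient 20, not whether safety is watched.

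**What to change.** Delete the parenthesis that limits the criterion to 10 or 20 recipients, and replace the broad-scope sentence with one table from the same bound: 4/10, 7/20, 8/30, 10/40, 12/50, 13/60, 15/70, 17/80, 18/90, 20/100, 21/110. Keep the existing convention that the study stops as soon as a count is reached. State that the table is the complete rule and that deaths and PNF are counted separately. Align the DSMB charter if needed.

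This is a practical version of the broader scope rather than either scope as written: it does not stop at 2/2, 3/5 or 5/14. If the sponsor means every count, the thresholds should be listed at every count.

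The change needs no extra patients or data. Its price is more stopping at a true rate of exactly 12%: 7.5% rather than 2.7% per endpoint (0.8% rather than 0.6% at 8%). With both endpoints at 12%, the study-level figure runs from full overlap of stops to none: 2.7% to 2 × 2.70 = 5.4% for the list, and 7.5% to 2 × 7.46 = 14.9% for the table.

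The alternative is to delete the broad-scope sentence and state that only DSMB judgement applies after recipient 20. That is equally simple to write, but it gives up numerical stopping after that point: at a 20% rate the stop probability stays at 15.7%.
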